#### 7.1.3 Rules for Early Termination

Bayesian probability calculations will be employed to define rules of early termination for feasibility and safety. The tables below indicate termination rules after groups of 3 patients have been treated, although the Bayesian probability of an event may be calculated at any time during the trial. Hundreds of patients with certain types of cancer have undergone radiation therapy with protons. Thus, we will assume a modest amount of "prior" feasibility and safety data for proton for our Bayesian calculations. We will assume prior information equivalent to that of 6 treated patients, which is commonly required to establish safety in a standard 3+3 Phase-I trial design.

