#### 7.1 FEASIBILITY STUDY

# 7.1.1 Design and Objectives

The primary objectives are to determine feasibility and safety (acute toxicity). Secondary objectives are to determine late toxicity, long-term clinical outcomes and, fatigue and neurocognitive function.

Twelve patients will be enrolled and followed for a minimum of 90 days after start of radiotherapy to determine feasibility and acute toxicity. We expect to screen/enroll approximately 18 subjects to reach the goal of 12 evaluable subjects. A subject will be considered evaluable if they willingly remain on the study up until their first follow up visit. [note: a subject is still evaluable even if they are unable to undergo proton treatment as defined in section 2.0 or have a significant acute toxicity as these are feasibility criteria]. Ninety days of observation after start of radiotherapy will be required in all 12 patients prior to commencing the second phase of the trial. Patients enrolled in the feasibility study will continue to be followed beyond 90 days for the secondary endpoints of late toxicity, progression-free and overall survival fatigue and neurocognitive function.

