### 7.1.2 Endpoints

### 7.1.2.1 Primary Endpoints

Feasibility will be based on multiple radiation planning and treatment parameters. For proton to be deemed feasible, no greater than 10% of patients should experience one of the following events: a) Patient cannot be given treatment because anatomy is such that a dosimetrically satisfactory treatment plan cannot be devised. For example, the dosimetry is unsatisfactory if

<95% of target volume is covered by 95% of the dose, b) Patient receives greater than 50% of their total treatment (for any reason-unable to set patient up within acceptable limits of tolerance, patient unable to tolerate treatment position or immobilization for duration of treatment) with photon beam radiotherapy (using a backup photon plan, c) Patient is unable to complete all of his/her treatments within 10 days of estimated date of treatment completion or requires a treatment break greater than 5 days.

Acute Toxicity is defined as any grade 3 or higher toxicity, considered probably or definitely related to radiation, observed within 90 days from start of therapy, excluding cranial nerve palsies or nerve root symptoms as these may be due to the tumor itself or prior surgery. Toxicities will be graded using the NCI Common Terminology Criteria for Adverse Events (CTCAE) Version 4.0.

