#### **Feasibility**

A feasibility rate  $\geq 90\%$  is considered acceptable. We will assume a beta (5,1) prior, which is information equivalent to feasibility established in 5 of 6 treated patients. If the number of patients in whom proton is deemed feasible is less than or equal to the number in the table below then termination will be considered as it is highly unlikely that the feasibility rate is  $\geq 90\%$ , as noted by the Bayesian posterior probabilities.

D ' D 1	C D '1 '1'	• ,				
Bayesian Rule	for Feasibili	ıty				
Patients treated in each stratum	3	6	9	1		
				2		
Patients in whom proton is	1	4	6	9		
feasible						
Posterior Prob[feasibility rate	0	0	0	0		
>90%]		•	•	•		
	0	0	0	0		
	4	9	4	8		
Action	Т	Terminate enrollment				

Acute toxicity will be divided into 2 categories to best characterize toxicities in this disease. Non-Neurologic Acute Toxicity

Because proton therapy is expected to spare normal tissues, a non-neurologic acute toxicity rate  $\leq 20\%$  is considered acceptable. We will assume a beta (1,5) prior, which is information equivalent to toxicity in of treated patients. If the number of patients with non-neurologic acute toxicity equals or exceeds the number in the table, then termination will be considered as it is likely that the toxicity rate is >10%, as noted by the Bayesian posterior probabilities.

Bayesian Rule for Non-Neurologic Acute Toxicity						
Patients treated	3	6	9	1		
				2		
Patients who experience acute	2	2	3	4		
toxicity						
Posterior Prob[toxicity rate	0	0	0	0		
>20%]			•			
	8	6	7	7		
	0	2	0	6		
Action	Te	Terminate enrollment				

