### 7.2.3 Rules for Early Termination; continuation of rules as in 7.1.3

#### Non-Neurologic Acute Toxicity

If the number of patients with non-neurologic acute toxicity equals or exceeds the number in the table, then termination will be considered as it is likely that the toxicity rate is >20%, as noted by the Bayesian posterior probabilities.

Bayesian Rule for Non-Neurol	logic A	Acute Toxicit	У	
Patients treated	1	2	3	4

Version: 04/04/2014

Patients who experience acute toxicity Posterior Prob[toxicity rate >20%]	5 5 0	5 7 0	5 9 0	5 1 1 0
2070]	8	7	7	7
Action	0   T	6 Cerminate e	nrollment	1

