#### 7.3 SAMPLE SIZE/POWER AND TRIAL DURATION.

Twelve evaluable patients will be enrolled on the feasibility portion of the trial. We estimate having to screen/enroll 18 subjects to reach the goal of 12 evaluable subjects. If feasibility and safety are acceptable, then an additional 38 patients will be enrolled for a study total of 50 patients. We may have to screen/enroll up to 50 subjects to have an additional 38 patients participate in the phase II portion of the trial. We estimate that the first 12 patients will be enrolled in 1 year. Then the study will be suspended for patient observation for 2 months for feasibility and safety evaluation. If the feasibility study is acceptable, then accrual will continue. With an accrual of 12 patients per year, the study should be actively enrolling for 4 years. To test whether the 12 month rate of severe fatigue is lower than 50%, a one sample test will be performed. With 50 patients, there is 79% power to detect a 33% rate versus a null rate of 50% by chi-square test at 1-sided 5% significance.

For the feasibility study, the initial target sample size of 12 patients will be revised to 12 additional base of skull patients to be treated with pencil beam protons and evaluated for feasibility by the new definition. There will not be a target sample size for spine patients and we will enroll those patients while filling the enrollment goal for the base of skull patients. It is anticipated that up to 5 spine patients may be enrolled. The total enrollment to the feasibility study after this amendment will be up to 17 patients (12 base of skull and 5 spine).

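### The acute-toxicity stopping tables count patients *treated*, an undefined term, while the endpoint takes 90 days, so outside the 12-patient look a boundary can be delayed or lost

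*Combined protocol and SAP*

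**What the plan says.** **Trigger.** Section 7.1.3 of the combined protocol and SAP states: "The tables below indicate termination rules after groups of 3 patients have been treated". The feasibility-phase toxicity tables have looks at 3, 6, 9 and 12 patients treated. Section 7.2.3 continues them at 15, 25, 35 and 45, with the same kind of trigger: "If the number of patients with non-neurologic acute toxicity equals or exceeds the number in the table", termination is considered. Nothing says whether *treated* means started, completed or observed to the end of the window.

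**Endpoint.** Section 7.1.2.1 counts acute toxicity "observed within 90 days from start of therapy". Under 6.1 toxicity is assessed weekly during radiotherapy and then at an inspection visit at about day 90.

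**Hold.** Section 7.1.1 states: "Ninety days of observation after start of radiotherapy will be required in all 12 patients prior to commencing the second phase of the trial". Sections 2 and 6.1 agree. No such condition is stated for the looks at 3, 6, 9, 15, 25, 35 or 45. No text says how a patient with less than 90 days of observation is counted.

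**Unscheduled calculations.** Section 7.1.3 adds: "although the Bayesian probability of an event may be calculated at any time during the trial". It gives no posterior cutoff for such a calculation.

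**The concern.** A beta-binomial stopping rule assumes that each patient in the denominator has a known outcome. If a row is read on the day the nth patient counts as treated, the most recent patients may still have weeks of their window to run. Any of them without a toxicity so far adds to the non-event count, and the posterior is lower than it will be once their outcomes are known.

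A later look does not always repair this. The boundary rises with n, so one event that would have met an earlier row can fall short of the next. What is at stake is a patient-safety rule: accrual could continue past a point at which the plan's own table calls for termination to be considered.

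**Working it through.** **1. Reproduce the plan's figures.** The prior is Beta(1,5) for both toxicity types (7.1.3). With x events in n patients, the posterior is Beta(1+x, 5+n−x).

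- Non-neurologic, P(rate > 20%) at 2/3, 2/6, 3/9, 4/12: 0.797, 0.617, 0.698, 0.758. The table has 0.80, 0.62, 0.70, 0.76.
- Neurologic, P(rate > 10%) at 1/3, 1/6, 2/9, 2/12: 0.813, 0.697, 0.842, 0.762. The table has 0.81 (first digit not legible in the copy reviewed), 0.70, 0.84, 0.76.

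The match requires every patient in n without an event to be a full non-event. So if a patient is put into n before day 90, the calculation treats that patient as toxicity-free.

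**2. How many windows are open.** Accrual is 12 per year (7.3), or 12–15 (3.3). Patients starting within any 90 days: 12/365 × 90 = 3.0, up to 15/365 × 90 = 3.7. If *treated* means radiotherapy completed, at up to 9 weeks (4.6, day 63), 27 days remain: 12/365 × 27 = 0.9, up to 15/365 × 27 = 1.1.

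**3. A boundary lost for good.** Suppose one of patients 1–6 has a neurologic toxicity that surfaces after the 6-patient look, and it is the only event in the first nine.

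- At the 6-patient look: 0/6, posterior 0.314, no trigger.
- At the 9-patient look: 1/9, posterior 0.585, boundary of 2 not met.
- With full windows: 1/6, posterior 0.697, a listed trigger.

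**4. Size by hand at the 3-patient neurologic look.** The boundary is 1 event. Assume a true rate of 20%, event times uniform over 90 days, and starts 365/12 = 30.4 days apart.

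- Full windows: 1 − 0.8³ = 0.488.
- *Treated* = completed: only the third patient's window is open, at day 63 of 90. 1 − 0.8² × (1 − 0.2 × 0.70) = 0.450.
- *Treated* = started: follow-up is 60.8, 30.4 and 0 days. 1 − (1 − 0.2 × 0.676)(1 − 0.2 × 0.338) = 0.194.

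**5. Size by the 9-patient look.** With full windows, no neurologic crossing means 0 events in patients 1–6 and at most 1 in patients 7–9. At 20% the chance of crossing is 1 − 0.8⁶ × (0.8³ + 3 × 0.2 × 0.8²) = 1 − 0.262 × 0.896 = 0.765. The other two readings were simulated on the same assumptions.

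| Assumed true rate | Full windows | Completed | Started |
|---|---|---|---|
| Neurologic 10% | 48% | 47% | 37% |
| Neurologic 20% | 77% | 75% | 63–64% |
| Neurologic 30% | 91% | 90% | 81% |
| Non-neurologic 30% | 65% | 62% | 45% |

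If every event appears by day 63 and *treated* means completed, the loss is zero.

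**6. What the protected 12-patient look recovers.** With that look fully observed, crossings never made up are 0.5 points (completed) or 3.4 points (started) for neurologic toxicity at 20%. For non-neurologic toxicity at 30% they are about 1.4 and 9 points. Over the four phase II looks taken alone, with the printed counts, they are 0.5 and 3.9 points (neurologic, 20%) and 0.6 and 4.9 points (non-neurologic, 30%).

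**The case against.** Several points on the other side are sound.

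- **The plan never says that pending patients count as toxicity-free.** A reader might infer that it does, but the text is silent. The effect arises only if such patients are entered in n. One could also read each row as referring to its patients' eventual 90-day outcomes. Section 7.1.1 calls a subject evaluable on remaining in the study to the first follow-up visit, which points that way but is not tied to the tables. So the defect is an ambiguity, not a stated miscount.
- **The natural reading of *treated* is treatment completed.** The loss by the 9-patient look is then 1 to 3 points in the cases above. A reader might take the larger drop as the finding, but it requires *treated* to mean started.
- **The look that opens phase II is protected** by the required 90 days in all 12 patients.
- **Other safeguards exist:** weekly assessment, serious adverse event reporting to the DSMC, and a Medical Monitor who may recommend suspension. The tables only prompt consideration of termination. These soften the risk, but they do not define the denominator or settle the interval from the end of radiotherapy to day 90.
- **The comparison is not at equal calendar time.** A fully observed look falls later, when about three more patients may have started.

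A further tempting reading is that 9 treated, 6 of them with closed windows, and 1 neurologic event always conceals a met boundary. It does not. If the event was in patients 1–6 and known at the 6-patient look, the rule had already triggered. If it was in patients 7–9, the 6-patient row was never met. Only the case in step 3 of the working fits.

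The option to calculate at any time does not answer the concern. It is discretionary, has the same undefined denominator and has no cutoff; the posteriors at the feasibility-phase toxicity boundaries run from 0.62 to 0.84.

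**Conclusion.** The concern holds as a real but limited gap. At the looks at 3, 6, 9, 15, 25, 35 and 45, the index of the toxicity tables does not match the 90-day endpoint, and a boundary can be delayed or permanently missed. At a true neurologic rate of 20%, the loss by the 9-patient look is about 2 points if *treated* means completed, about 13 if it means started, and nil if it means completed and all events have appeared by then. True rates, even accrual and uniform event times are assumptions; the documents give only the accrual rate, the treatment duration and the window.

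The documents do not support the stronger claims that the plan instructs unfinished patients to be counted as free of toxicity, or that the rule as a whole is ineffective. The case for change is that the performance of a safety rule should not depend on an undefined word when defining it costs little.

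**What to change.** **Wording for 7.1.3 and 7.2.3.** State that row n applies to the first n patients in enrollment order. The boundary is met as soon as their known toxicities reach the tabled number. The row is passed only when all n have completed 90 days from the start of radiotherapy, and it is re-checked when the last window closes. Say how a patient who leaves before day 90 without toxicity is handled. Label any unscheduled posterior that includes open windows as provisional.

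This gives the full-window crossing probabilities by construction.

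**What to avoid.** Do not define n as patients who have completed 90 days or already had a toxicity. That counts events at once and non-events only at day 90, which biases the rate upward. In simulation, triggering by the 9-patient look rises from 48% to 53% at the acceptable neurologic rate of 10%, and from 39% to 44% at the acceptable non-neurologic rate of 20%.

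**Cost.** No new visits, data or mandatory accrual pause. A result of *no stop* is confirmed up to 90 days later, during which about 3 to 4 further patients may start.

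**To reconcile at the same time.**
- Section 7.2.1 says phase II has no early stopping, while 7.2.3 gives stopping tables for it.
- Section 7.3 says "Then the study will be suspended for patient observation for 2 months for feasibility and safety evaluation", against the 90 days in 7.1.1.
- Section 8.1 runs acute effects to day 90 after treatment, not from its start.
- The printed phase II neurologic posteriors (0.68, 0.82, 0.79, 0.77) match counts of 2, 4, 5, 6, one below the printed 3, 5, 6, 7. This is a separate matter, but it affects the same rows.

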#### **Feasibility**

A feasibility rate  $\geq 90\%$  is considered acceptable. We will assume a beta (5,1) prior, which is information equivalent to feasibility established in 5 of 6 treated patients. If the number of patients in whom proton is deemed feasible is less than or equal to the number in the table below then termination will be considered as it is highly unlikely that the feasibility rate is  $\geq 90\%$ , as noted by the Bayesian posterior probabilities.

D ' D 1	C D '1 '1'	• ,				
Bayesian Rule	for Feasibili	ıty				
Patients treated in each stratum	3	6	9	1		
				2		
Patients in whom proton is	1	4	6	9		
feasible						
Posterior Prob[feasibility rate	0	0	0	0		
>90%]		•	•	•		
	0	0	0	0		
	4	9	4	8		
Action	Т	Terminate enrollment				

Acute toxicity will be divided into 2 categories to best characterize toxicities in this disease. Non-Neurologic Acute Toxicity

Because proton therapy is expected to spare normal tissues, a non-neurologic acute toxicity rate  $\leq 20\%$  is considered acceptable. We will assume a beta (1,5) prior, which is information equivalent to toxicity in of treated patients. If the number of patients with non-neurologic acute toxicity equals or exceeds the number in the table, then termination will be considered as it is likely that the toxicity rate is >10%, as noted by the Bayesian posterior probabilities.

Bayesian Rule for Non-Neurologic Acute Toxicity						
Patients treated	3	6	9	1		
				2		
Patients who experience acute	2	2	3	4		
toxicity						
Posterior Prob[toxicity rate	0	0	0	0		
>20%]			•			
	8	6	7	7		
	0	2	0	6		
Action	Te	Terminate enrollment				

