#### **Primary Objective**

The primary objective of this study is feasibility. The study will be deemed infeasible if greater than 10% of pts experience one of the following:

- a. Patient cannot be given treatment because anatomy is such that a dosimetrically satisfactory treatment plan cannot be devised as defined in Section 4.5.1.
- b. For base of skull patients only. Patient receives greater than 40% of their total treatment (for any reason, i.e. unable to set patient up within acceptable limits of tolerance, patient unable to tolerate treatment position or immobilization for duration of treatment) with photon beam radiotherapy (using a backup photon plan).

For spine and all other patients. Patient receives greater than 20% of their total treatment (for any reason, i.e. unable to set patient up within acceptable limits of tolerance, patient unable to tolerate treatment position or immobilization for duration of treatment) with photon beam radiotherapy (using a backup photon plan).

- c. Patient is unable to complete all of his/her treatments within 10 days of estimated date of treatment completion or requires a treatment break greater than 5 days.
- d. Additionally, no greater than 20% of patients experience an unexpected acute toxicity > Grade 3 that is probably or definitely related to radiation therapy.

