### 7.1.4 Statistical Analyses

Feasibility. The initial target sample size of 12 patients will be revised to 12 additional base of skull patients to be treated with pencil beam protons and evaluated for feasibility by the new definition. It is anticipated that up to 5 additional spine patients may be enrolled. So the total enrollment after this amendment will be up to 17 patients (12 base of skull and 5 spine). The statistical analysis will calculate the posterior probability that the feasibility rate is >90%. This analysis will be conducted 2 ways: based on all 26 patients treated and on all 17 patients treated after the modification. The definition of infeasibility will be that which was current when the patient enrolled on the trial. There will be no retroactive re-grading of infeasibility in the base of skull patients.

Acute Toxicity. All toxicities observed within 90 days from start of therapy will be graded by CTC Version 4.0 and tabulated. Special attention is paid to neurologic toxicity.

Late Toxicity. All toxicities observed later than 90 days from start of therapy will be graded by the CTCAE version 4.0 and tabulated.

Progression-free and overall survival will be estimated by the survival analysis methods. It is most likely that these time-to-event outcomes will be summarized as part of the phase II study.

Fatigue is scored on a 10-point scale based on the Brief Fatigue Inventory Questionnaire. At each time point, the BFI score will be summarized by mean and standard deviation, and plotted over time. We will examine the plots for the expected worsening of function in the 6-12 months post-radiation and gradual improvement from 12-24 months. The fatigue scores will be summarized in detail in the phase II study.

Neurocognitive function (FACT-Br) will be summarized by descriptive statistics and scatter plots. It is most likely that the neurologic outcomes will be summarized as part of the phase II study.

Estimation of Event Rates. The table below displays the 90% exact binomial confidence

intervals based on 12 patients treated.

intervals ous	ed on 12 patients	i catea.			
No. of	%	90%	No. of	%	90%
Events		exact	Events		exact
		CI			CI
0	0.0	17.5*	7	58.3	31.5,
					81.9
1	8.3	.43,	8	66.7	39.1,
		33.9			87.7
2	16.7	3.0,	9	75.0	47.2,
		43.8			92.8
3	25.0	7.2,	10	83.3	56.1,
		52.7			97.0
4	33.3	12.3,	11	91.7	66.1,
		60.9			99.6
5	41.7	18.1,	12	100.0	82.5*
		68.5			

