#### 7.2 PHASE II STUDY

Once feasibility and safety are established in the first 12 patients, then the phase II study will commence.

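### At 12 patients the plan has two feasibility thresholds: above 10% infeasible under the primary criterion, but 3 of 12 (25%) in the Section 7.1.3 table, so the verdict at 2 of 12 is not settled

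*Combined protocol and SAP*

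**What the plan says.** **The primary criterion.** Section 2, Primary Objective: "The study will be deemed infeasible if greater than 10% of pts experience one of the following", followed by the list of events. Section 7.1.2.1 gives the same limit: "For proton to be deemed feasible, no greater than 10% of patients should experience one of the following events". The opening paragraph of Section 2 says the primary objectives are the means of settling feasibility, and that the second phase waits until safety and feasibility have been verified.

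**The table.** Section 7.1.3 gives early-termination rules after each group of three patients. For feasibility: "We will assume a beta (5,1) prior, which is information equivalent to feasibility established in 5 of 6 treated patients". If the number feasible is at or below 1 of 3, 4 of 6, 6 of 9 or 9 of 12, "then termination will be considered as it is highly unlikely that the feasibility rate is" at least 90%. The printed posterior probabilities of a feasibility rate above 90% at those counts are 0.04, 0.09, 0.04 and 0.08.

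**The gate.** Section 7.2: "Once feasibility and safety are established in the first 12 patients, then the phase II study will commence". Section 7.3 adds the 38 further patients if feasibility and safety are *acceptable*. Section 7.1.3 uses that same adjective for a feasibility rate of at least 90%. Neither 7.2 nor 7.3 cites a rule.

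**The final analysis after the amendment.** Section 7.1.4 sets a new sample of 12 base of skull patients plus up to 5 spine patients, and says "The statistical analysis will calculate the posterior probability that the feasibility rate is >90"%, once on all 26 patients and once on the 17 treated after the change. It gives no value of that probability that means feasible.

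**The concern.** Feasibility is the primary objective and decides whether 38 more patients are enrolled. The last column of the table is read when the feasibility cohort is complete, so it falls at the same moment as the primary criterion but uses a different threshold. A result of 2 of 12 lies between the two: the primary criterion calls it infeasible, and the table takes no action. Because Sections 7.2 and 7.3 do not say which rule opens phase II, the reading of that result could be chosen after it is known. The amendment adds to this: the table stops at 12 patients, Section 7.2 still speaks of the first 12, and the 17- and 26-patient analyses have no cut-off.

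**Working it through.** **1. Reproduce the table.** With a beta(5,1) prior and x infeasible among n patients, the posterior for the feasibility rate is beta(5 + n − x, 1 + x). Its probability above 0.90 equals Pr[Bin(n + 5, 0.10) ≥ x + 1].

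- 1 of 3 feasible (x = 2): 0.038
- 4 of 6 (x = 2): 0.090
- 6 of 9 (x = 3): 0.044
- 9 of 12 (x = 3): 0.083

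These match the printed 0.04, 0.09, 0.04 and 0.08.

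**2. Compare the thresholds at 12.** 1/12 = 8.3% meets the 10% limit, 2/12 = 16.7% fails it, and 3/12 = 25% is where the table acts. At 2 of 12 the plan's posterior is Pr[Bin(17, 0.10) ≥ 3] = 0.238, so odds of about 3 to 1 (0.762/0.238) that feasibility is below 90%.

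**3. When does 2 of 12 escape the table?** The boundaries are 2, 2, 3 and 3 infeasible at 3, 6, 9 and 12 patients. Two events cross a boundary only if both fall in the first six patients. That is C(6,2) = 15 of the C(12,2) = 66 orderings (23%), leaving 51 that cross nothing.

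**4. Chance of passing under each rule.** Let p be the true infeasibility rate. The documents give no expected value, so a range is shown.

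- 10% criterion (at most 1 of 12): A = (1 − p)^12 + 12p(1 − p)^11. The interim looks do not alter this, because 0 or 1 event never crosses a boundary.
- Disputed results (2 of 12, no boundary crossed): B = 51p²(1 − p)^10.
- Table treated as a binding gate: A + B.

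| True p | A: 10% criterion | B: disputed | A + B: table |
|---|---|---|---|
| 5% | 88.2% | 7.6% | 95.8% |
| 10% | 65.9% | 17.8% | 83.7% |
| 15% | 44.3% | 22.6% | 66.9% |
| 20% | 27.5% | 21.9% | 49.4% |
| 25% | 15.8% | 17.9% | 33.8% |

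With p = 0.20: A = 0.0687 + 0.2062 = 0.2749; B = 51 × 0.04 × 0.1074 = 0.2190; the sum is 0.4939. If only the 12-patient look is applied, because termination at the earlier looks is merely considered, 55.8% pass at p = 0.20.

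**5. The amended sample.** The 10% limit allows 1 of 17 (5.9%; 2 of 17 is 11.8%) and 2 of 26 (7.7%; 3 of 26 is 11.5%). The posterior at the largest allowed count is 0.518 for 12, 0.661 for 17 and 0.611 for 26. One more event gives 0.238, 0.380 and 0.376.

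**The case against.** The strongest reply is that Section 2 already names the governing rule. Its opening ties the settling of feasibility to the primary objectives, the first of which is the 10% limit, and Section 7.1.2.1 states the same limit as a positive condition. The table sits under a heading on early termination, and a stopping boundary looser than the final success criterion is ordinary design. On this view 2 of 12 simply fails.

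Most of that stands. A reader might infer that the plan opens phase II whenever no boundary is crossed, and so passes a true 20% infeasibility rate about half the time. No sentence says so. The 49% applies only if the table is used as the gate and treated as binding; under the criterion in Section 2 the figure is 27%. A reader might also carry the table's cut-off of about 0.09 over to the 17- and 26-patient analyses, but the plan sets no cut-off there. Nor can it be said that 12 patients can never exclude a 20% rate: the plan's own interval table gives a one-sided upper limit of 17.5% for 0 of 12.

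What the reply does not remove is the 12-patient column. A look at the end of the cohort is no longer an early one, and it carries a different threshold from the primary criterion. Sections 7.2 and 7.3 do not refer back to Section 2, and Section 7.1.4 makes the final analysis a posterior with no decision value.

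**Conclusion.** The plan holds two thresholds for the primary endpoint at 12 patients, and its phase II gate does not say which applies. Section 2 favours the 10% criterion, so this is a conflict to be reconciled, not proof that the gate is lax. The result at issue is 2 of 12 with the events not both in the first six patients; it would arise in 18% of trials at a true rate of 10%, 23% at 15% and 22% at 20%. The choice of rule moves the chance of passing at an assumed true 20% between 27% and 49%. These figures assume independent patients with a constant event rate and binding boundaries. The gap after the amendment is separate and needs no assumption: neither the deciding set (17 or 26) nor a decision value is stated.

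**What to change.** 1. Label the Section 7.1.3 feasibility table as interim stopping only, at 3, 6 and 9 patients. Remove the 12-patient column, or change its 9 to 10. Removal is cleaner: with 10 the printed posterior would become 0.24, which no longer fits the text's description of a rate of 90% or more as highly unlikely.
2. State in Sections 7.2 and 7.3 that phase II opens only if no more than 10% of patients are infeasible, as in Section 2, and that not crossing an interim boundary does not count as feasibility.
3. In Section 7.1.4, say whether the 17- or the 26-patient set decides, and apply the same limit: at most 1 of 17 or 2 of 26. Report the posterior and an exact confidence bound beside the verdict.

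**Cost.** Wording only, with no extra patients. The strict criterion has a price that should be disclosed. The chance of a not-feasible verdict is:

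| True rate | 12 patients | 17 patients | 26 patients |
|---|---|---|---|
| 10% | 34% | 52% | 49% |
| 5% | 12% | 21% | 14% |

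Each entry is 1 minus the binomial probability of at most 1, 1 or 2 events. Under the table the 12-patient figure at a true 10% is 16%. These risks follow from the criterion the plan already states. One side effect remains: with the 9-patient boundary left at 3 infeasible, a 12-patient cohort whose second event comes at patient 7 keeps enrolling although it can no longer meet the final criterion. The plan should say whether that is intended.
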